**Instruction:**  
Start in warrior one, bend the knee of the back leg a little, lengthen your tailbone towards the floor. Stretch through your back leg, opening and stretching the sole of the foot. Open your chest and draw your front ribs down into your torso. Stay in this position for five breaths.

		hand down to the floor or to a yoga block placed in front of your foot.			
--	--	--	--	--	--


Balance pose
	
Activity:            (1) Tree pose, (2) Standing holding knee, (3) Modified warrior three (chair support), (4) Half moon.
 
Maximum duration: 15 minutes
 
Purpose:
 
 
• Strengthening and lengthening the muscles.
 
• Exploring your center of gravity and improving the body's equilibrium.
 
• Improving focus, concentration, and memory and relieving stress
 
	
  
   
1. Tree poses
 	  
2. Standing holding knee
 	  
3. Modified warrior 3 (Chair support)
 	
 
  
Instruction:            Begin in mountain pose. Shift your weight onto your left leg. Bend your right knee and place your right foot on the inside of your left leg, either above or below the knee joint, pressing your foot against your inner thigh. Pull your left hip in over your left foot (use chair or wall to help balance if needed). Lengthen your spine, loosen shoulders and tuck your chin slightly in and back, bringing
 	 
Instruction:            Begin in mountain pose. Place your left hand on your hip. Moving very slowly, draw your right knee up towards your chest. With your right hand, hug your knee to your chest. Lengthen your spine, tightening the muscles of your left side and abdomen. Stiffen your left leg, but do not lock your knee. Drop your right hip slightly until it is in line
 	 
Instruction:            Begin with warrior one on the right side. Bring your palms together and begin to lean forward. Lift the left leg off the floor, keeping the body, arms, and raised left leg parallel to the floor, flexing the toes. Strenghten the standing leg and your arms. Fix your gaze looking down, hold the pose and breathe. Then lower your leg back down into warrior 1 position, then practice on the other side.
 	
  
	 
1. Tree poses
	 
2. Standing holding knee
	 
3. Modified warrior 3 (Chair support)
	
Instruction:            Begin in mountain pose. Shift your weight onto your left leg. Bend your right knee and place your right foot on the inside of your left leg, either above or below the knee joint, pressing your foot against your inner thigh. Pull your left hip in over your left foot (use chair or wall to help balance if needed). Lengthen your spine, loosen shoulders and tuck your chin slightly in and back, bringing
	
Instruction:            Begin in mountain pose. Place your left hand on your hip. Moving very slowly, draw your right knee up towards your chest. With your right hand, hug your knee to your chest. Lengthen your spine, tightening the muscles of your left side and abdomen. Stiffen your left leg, but do not lock your knee. Drop your right hip slightly until it is in line
	
Instruction:            Begin with warrior one on the right side. Bring your palms together and begin to lean forward. Lift the left leg off the floor, keeping the body, arms, and raised left leg parallel to the floor, flexing the toes. Strenghten the standing leg and your arms. Fix your gaze looking down, hold the pose and breathe. Then lower your leg back down into warrior 1 position, then practice on the other side.

 
1. Tree poses
	 
2. Standing holding knee
	 
3. Modified warrior 3 (Chair support)
						

Instruction:            Begin in mountain pose. Shift your weight onto your left leg. Bend your right knee and place your right foot on the inside of your left leg, either above or below the knee joint, pressing your foot against your inner thigh. Pull your left hip in over your left foot (use chair or wall to help balance if needed). Lengthen your spine, loosen shoulders and tuck your chin slightly in and back, bringing
	
Instruction:            Begin in mountain pose. Place your left hand on your hip. Moving very slowly, draw your right knee up towards your chest. With your right hand, hug your knee to your chest. Lengthen your spine, tightening the muscles of your left side and abdomen. Stiffen your left leg, but do not lock your knee. Drop your right hip slightly until it is in line
	
Instruction:            Begin with warrior one on the right side. Bring your palms together and begin to lean forward. Lift the left leg off the floor, keeping the body, arms, and raised left leg parallel to the floor, flexing the toes. Strenghten the standing leg and your arms. Fix your gaze looking down, hold the pose and breathe. Then lower your leg back down into warrior 1 position, then practice on the other side.
						

your hands in front of your heart (prayer position). Stay in this pose for 30 seconds or 1 minute, then repeat on the other side.

[figure not shown]
[figure not shown]
with your left hip. Hold for 1 minute.

4. Half-moon pose (chair support)

Instruction:  
Start in warrior 2 with a chair beside you. Bring your right hand to your hip and turn your head to look at the floor. Bend your front leg and shift your weight onto your front foot. Move your hand a little forward and place your forearm on the chair

directly beneath your shoulder. Press down through your fingers to steady yourself. Lift your back leg until your thigh is parallel to the floor. Slowly turn your chest to face the right. Extend your other arm toward the ceiling. Either keep your gaze on the floor or slowly bring it to your hand above.


Abdominal and back bends
	
Activity: (1) Bird-dog, (2) Side plank, (3) Bridge, (4) Cobra, (5) Sphinx.
 
Duration: 10 minutes
 
Purpose:
 
 
• Lengthen and strengthen spine, promoting flexibility, mobility, and good posture.
 
• Stretch shoulders, chest, and abdomen.
 
• Reduce stress and anxiety.
 
	
 
  
1. Bird-dog
 
 
  
2. Side plank
 
 
  
3. Bridge
 
 
 
 
 
Instruction:
 
Begin with hands and knees on the floor in the tabletop position, with knees under hips and hands under your shoulders. Maintain a neutral spine by firming up your abdominal muscles. Draw your shoulder blades together, raising right arm and left leg. Keeping shoulders and hips parallel to the floor, extend the back of your neck and tuck your chin into your chest to gaze down at the floor. Hold this position for a
 
 
 
Instruction:
 
Begin with plank pose (with your weight on both forearms) and press your palms into the mat as you lift up through your shoulder. Turn onto the outside of your right foot, stacking your left foot on top of it. Rotate your entire body to face forward with your flank toward the floor. Press your right hand down, keeping your body even from heel to fingers, as you raise your left arm up toward the sky. Take 5 to 10 deep breaths.
 
 
 
Instruction:
 
Lying on your back, place your feet flat on the floor, with your arms next to your ribcage. Inhale and press the back of your shoulders and your feet into the floor and lift your hips. Actively press the inside of feet down and keep your knees from spreading out wide. You're your belly in and slide your shoulder blades down your back, keeping your neck neutral. You can clasp your hands
 
 

---------------------------------	--	--

few seconds, then do the other side.
		
behind your back. Stay in this position for 5 to 15 breaths.
	
	
4. Cobra
		
5. Sphinx


Introduction: Lie on your stomach, with your toes pointing straight back. Position your hands underneath your shoulders, with elbows close to your body. With legs engaged, pull the belly in and up, lifting your chest from the back of your heart. Sticking your chest out, pull your shoulder blades together and down along the spine. Come down
	
Introduction: Lying down on your belly with your shoulders over your elbows, with your forearms flat on the floor. Bring your shoulder blades together sliding down your back and feel your chest pushing slightly forward. Breathe into your lower back and abdomen. To come out of the pose, lower your torso, bringing your elbows toward your sides and
	
Introduction: Place your hands and knees on the mat. Spread your knees the same width as the mat and extend your big toe with your big toe on the floor. Place your stomach between your thighs and your forehead on the floor. Relax your shoulders, chin and eyes. If you're not good at putting your forehead on the floor, put your forehead on a
	

		gradually as you exhale. Repeat that two times.	rest your forehead on your hands.	stack of fist blocks or two	
Cool down	
Activity:
 
(1) Twist, (2) Cobbler's pose, (3) Hip stretches, (4) Corpse pose, (5) Side-lying, (6) Seated on.
 
Duration: 10 minutes
 
Purpose:
 
 
• Gradually slow down allowing heart rate to return to normal, preventing muscle soreness.
 
• Reduce stress and improve relaxation.
 
	 
1. Twist
	 
2. Cobbler's pose
	 
3. Hip stretches
	
Instruction:
 
Begin in seated meditation pose with right leg crossed on top of your left. Inhale and bring your right hand straight up beside your right ear. Exhale and twist your torso to the left, bringing your right elbow to the outside of your left knee and place your left palm on the floor slightly behind
 
Instruction:
 
Bend your knees and bring the soles of your feet together. As you let your knees fall down to either side, draw your feet in towards your body as far as you comfortably can. Press the outer edges of your feet together firmly. You can use your hands to pull
 
Instruction:
 
Lie on your back with your knees bent and feet flat on the floor. Bend your right knee until your lower leg is perpendicular to the floor. Then bring your left knee up, rotating your left leg outward at the hip so you can rest your left ankle on your right thigh just above the knee. Bring your right hand to the outside of the right thigh and pass your left

	
your sit bones. Direct your gaze over your left shoulder without straining your neck. On each inhale, lengthen your spine upwards. On each exhale, deepen the twist slightly.
	
your feet together and toward your body.
	
hand through the opening formed by your crossed left leg. As you pull your right thigh toward your chest with your hands, press your left thigh with your left elbow. Hold for 30 seconds.

	 
4. Corpse pose
	 
5. Side-lying
	 
6. Seated on

	
Introduction: Lie on your back. Separate your legs slightly and allow your feet to fall open to either side. Bring your arms down alongside your body, at a small distance from your torso. Turn your palms to face upwards but let the fingers curl in. Tuck your shoulder blades into
	
Instruction: Rest on the mat on your most comfortable side. Use your arm or a folded blanket to support your head and another to separate your knees. Roll the top hip slightly forward and shift the bottom hip slightly
	
Instruction: This seated meditation pose is the last pose of the yoga series, exactly the same as the first one. Hold this position for one minute.

		
your back. Once you have put your limbs in place, relax completely without making an effort to holding them in position. Relax your entire body, including your face. Feel the weight of your body against the floor.
	
back so the hip joints are not stacked on top of each other. Relax the belly and breathe slowly and deeply. Feel the breath in your body as you gently observe each inhale and exhale.
	
--	--	--	---	--

### **3. Statistical analysis plan**

Before performing statistical procedures, all data was entered into a computer and checked for errors. To analyze the data, the researcher then used SPSS computer software version 20. The data for all variables was manually coded before using the SPSS application, including demographic characteristics of patients, the perceived stress scale results brief health status survey, and coping self-efficacy. The alpha value was set at  $\alpha=0.05$  to determine the statistical significance of the variables. For demographic characteristics, the data analysis was descriptive statistics to identify the frequencies and percentages for categorical variables and the means and standard deviations for continuous variables. Before the statistical data processing begins, the data for independent and dependent variables was tested to determine its distribution and normality using plot histograms, logs and square roots, and checking residuals.

This study took repeated assessments over time and used a Generalized Estimating Equation (GEE) approach to model each study outcome and to predict the relationship of the variables while accounting for correlated data within the repeated measures (Hardin & Hilbe, 2007). The GEE technique, introduced by Liang and Zeger (1986), was the most often used strategy in marginal models, and it was a variation of Generalized Linear Modelling (GLM). GEE can handle correlated data with discrete, continuous, or binary outcomes. GEE is a non-likelihood or quasi-likelihood data modeling approach that specifies one of many working correlation matrix architectures to account for within-subject correlations (Liang & Zeger, 1986).

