**[name]**

**Advisor: [name] [name]**

**NCT Number: NCT05503680**

**Document date: January 7th, 20223**

## 1. Yoga protocol intervention

[figure not shown]
Participants in the yoga group engaged in eight biweekly online Hatha yoga classes for 120 minutes each at home. Classes began with 15 minutes of sitting meditation; breathing exercises; shoulder, neck, and back stretches; and sun salutations (either seated or standing). Following that, ten minutes of standing poses, fifteen minutes of balancing poses, and ten minutes of abdominal and back-bend positions will be performed. After 10 minutes of cool-down stretches and a final time of rest, all sessions was concluded. Physical postures and supportive props were modified to accommodate participants of all abilities. Participants was given an honorarium of Rp 50.000 or 3.49 USD at the baseline and final assessments. The full version of the yoga protocol is available in appendix III.

Table 3: Yoga protocol

Position	Main content	Length time
1. Warm-up	(1) Seated meditation, (2) Alternate (3) Nostril breathing, (4) Bellows breath, (5) Shoulder/neck stretches, (6) Cat-cow forward fold, (7) Sun salutations.	10 minutes
2. Standing poses	(1) Warrior one, (2) Warrior two, (3) Triangle, (4) Extended side angle, (5) Reverse warrior, (6) High lunge with twist.	10 minutes
3. Balance poses	(1) Tree pose, (2) Standing holding knee, (3) Modified warrior three (chair support), (4) Half-moon.	10 minutes

4. Abdominal and back bends	(1) Bird-dog, (2) Side plank, (3) Bridge, (4) Cobra, (5) Sphinx, (6) Baby position	10 minutes
5. Meditation	Full lotus, half lotus, Burmese	10 minutes
6. Cool down	(1) Twist, (2) Cobbler's pose, (2) Hip (3) Stretches, (4) Corpse pose, (5) Side-lying, (6) Seated on.	10 minutes

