**All rights reserved**

## **Preface**

This 60-minute yoga protocol was developed for participants in the research project, "The effect of a yoga intervention for reducing stress among people living with HIV during the covid-19 pandemic in Indonesia, a randomized controlled trial."

You have been given a copy of this protocol because you are an HIV positive person and are undertaking a yoga intervention program to reduce stress. This protocol has an instructor and pictures of yoga poses to help you to practice yoga correctly. Share this protocol with your family, friends, or community who might need help to recover from stress related to HIV.

[name]

Doctoral student

February 3rd, 202

Position	Activity/purpose	Action plan		
Warm up (15 minutes)	
Activity:            (1) Seated meditation, (2) Alternate nostril breathing, (3) Bellows breath, (4) Shoulder/neck stretching, (5) Cat-cow forward fold, (6) Sun-salutation.
 
Maximum duration: 15 minutes
 
Purpose:
 
 
• Warming up for hatha yoga aims to help participants to prepare their minds to be centered, calm, and focused.
 
• A distracted mind prevents participants from reaping the deepest psychological and spiritual benefits from yoga practice.
 
 
Equipment:            Yoga mattress, chair, sport clothes, chair
	 1. Seated meditation	 2. Alternate nostril breathing	 3. Bellows breath

		
coming in and going out, letting thoughts float away like logs rolling down the river.
	
through the right side. Next inhale through your right nostril, then close it as you open the left nostril and exhale through the left side. This is one cycle. Repeat 5 times.
	
inhalation happening in between. Make sure the breath comes from your diaphragm, with your belly moving in and out. head, neck, shoulders, and chest

		 
4. Shoulder/neck stretching
	 
5. Cat-cow forward fold
	 
6. Sun salutation

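### The SAP does not say how the baseline score enters the GEE or which yoga-minus-control contrast is the treatment effect; a baseline-adjusted difference would usually be more precise

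*Combined protocol and SAP*

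**What the plan says.** The inferential plan is one paragraph in section 3, Statistical analysis plan. It says "This study took repeated assessments over time" and that the study "used a Generalized Estimating Equation (GEE) approach to model each study outcome and to predict the relationship of the variables", allowing for within-person correlation. The outcomes listed for coding are "the perceived stress scale results brief health status survey, and coping self-efficacy". Alpha is 0.05 and is tied only to the need "to determine the statistical significance of the variables". GEE is then described in general terms, as a method that "specifies one of many working correlation matrix architectures to account for within-subject correlations"; no structure is chosen.

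Two facts come from elsewhere. Section 1, Yoga protocol intervention, mentions an honorarium paid "at the baseline and final assessments", so a baseline assessment exists. The Preface gives the study title, ending "during the covid-19 pandemic in Indonesia, a randomized controlled trial", so allocation is described as random.

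The SAP section names no group term, time term, group-by-time term, baseline covariate, common baseline mean, primary visit or yoga-minus-control estimate. This can be said only of the available text.

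**The concern.** GEE is an estimation method. It does not by itself say what is being estimated. The paragraph is compatible with at least three ways of obtaining a yoga effect:

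- a group-by-time coefficient, which compares changes from baseline;
- the plain difference between arms at the final visit;
- a difference that uses the baseline score for adjustment, as a covariate or through a common baseline mean.

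Under randomisation and with complete data, all three estimate the same mean difference. They will not give the same number in a given data set: with two visits, the first two differ by exactly the observed baseline difference between the arms. If the contrast is not named, it can be chosen after the results are seen.

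The contrasts also differ in precision. Randomisation makes the baseline means equal in expectation, so a baseline score that is already collected can be used to reduce variance. The plan does not say that it will be.

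**Working it through.** **Inputs.** From the documents: random allocation (Preface), a baseline and a final assessment (section 1), alpha 0.05 (section 3). Sidedness is not stated; two-sided is assumed. Also assumed, because the available text does not give them: total N = 40 in two equal arms, two visits, equal SDs at both visits, complete data, and baseline-to-final correlation ρ of 0.3, 0.5 or 0.7. The plan gives no power or precision figure to reproduce.

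**Variances**, in units of 2σ²/n with n per arm:

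- final-visit difference: 1
- group-by-time (change): 2(1 − ρ)
- baseline-adjusted: (1 − ρ²) × [1 + 1/(N − 4)]. The bracket is the cost of estimating one slope; at N = 40 it is 37/36 = 1.028.

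| ρ | adjusted | change | adjusted ÷ change | adjusted ÷ final |
|---|---|---|---|---|
| 0.3 | 0.91 × 1.028 = 0.935 | 1.40 | 0.67 | 0.94 |
| 0.5 | 0.75 × 1.028 = 0.771 | 1.00 | 0.77 | 0.77 |
| 0.7 | 0.51 × 1.028 = 0.524 | 0.60 | 0.87 | 0.52 |

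**In power terms** (noncentral t, two-sided 0.05, N = 40). If the adjusted analysis had 80% power, group-by-time would have 63%, 69% and 75%, and the final-visit difference 77%, 69% and 53%, at ρ = 0.3, 0.5 and 0.7.

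**Where adjustment loses.**

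- Against the final-visit difference: it loses when (1 − ρ²)(N − 3)/(N − 4) > 1, that is when ρ < 1/√(N − 3). The limit is 0.24, 0.16 and 0.10 at N = 20, 40 and 100. At N = 40 and ρ = 0.1 the ratio is 0.99 × 1.028 = 1.02.
- Against change, with equal SDs: it loses when ρ > 1 − 2/(N − 3), that is above 0.88, 0.95 and 0.98 at the same N.
- Against change, with unequal SDs: let k be final SD divided by baseline SD. The ratio is k²(1 − ρ²)/(1 + k² − 2ρk) × 37/36 at N = 40. With k = 1.25 it is 0.81, 0.92 and 1.01 at ρ = 0.3, 0.5 and 0.7, and it exceeds 1 for ρ of about 0.68 to 0.88, by at most 3%. A change score fixes the slope at 1, so it does best when the true slope, ρk, is near 1.

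**Common-baseline-mean GEE** (intercept, time, group × time). Whether this equals adjustment depends on the working correlation.

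- Under independence the fit is least squares on three free cell means: pooled baseline, control final and yoga final. The group × time coefficient is then exactly the unadjusted final-visit difference. Its variance relative to the adjusted estimate is 1/0.935 = 1.07, 1/0.771 = 1.30 and 1/0.524 = 1.91 at ρ = 0.3, 0.5 and 0.7.
- Under an exchangeable structure, simulation with equal SDs and complete data gave a variance ratio of 0.99 to 1.00 against the adjusted estimate.

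**Interval coverage.** In simulation, a 95% CI for the adjusted estimate from the uncorrected sandwich variance with a normal quantile covered 91%, 93% and 94% at N = 20, 40 and 100. HC3 with a t quantile covered 96%, 96% and 95%.

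**The case against.** The strongest reply is that this is partly silence and partly preference. The group-by-time and final-visit contrasts are valid, and a GEE on repeated assessments may well include the baseline score as one of its responses. The size of any gain rests wholly on assumed values. Some pages of the document were not available, and the SAP section is largely in the past tense, so the analysis may already have been done.

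Most of this stands and limits the point. Four stronger readings should be set aside:

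- A reader might infer that the plan ignores the baseline score. The text does not say so. Baseline could be a response, a covariate or absent; what is missing is a statement of which.
- A reader might infer that the plan would report a group coefficient averaged over visits including baseline, which with two visits would estimate half of the final-visit effect. Nothing in the documents plans this; it is only not ruled out.
- A reader might infer that adjustment always wins. It does not, as the break-even points show.
- A reader might infer that an intended common-baseline GEE already settles the matter. It does so only with a non-independence working correlation, and the SAP does not name one.

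What the reply does not remove is that the contrast is unnamed, and that a nearly free and usually more precise analysis of data already collected is not specified.

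**Conclusion.** The point holds as one of specification and efficiency. It does not show bias or an invalid analysis. The available SAP text leaves open how the baseline score is used and which contrast at which visit is the yoga effect.

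In the illustrated case (N = 40, two visits, equal SDs, complete data), baseline adjustment lowers variance by 33%, 23% and 13% against group-by-time, and by 6%, 23% and 48% against the final-visit difference, at ρ = 0.3, 0.5 and 0.7. It can be a few percent worse than the final-visit difference at very low ρ, or than change at high ρ or when the final SD exceeds the baseline SD. If a common-baseline GEE with, for example, an exchangeable structure was intended, there is essentially no gain left and a sentence saying so would close the point. The change should be made; confidence is medium, because N, SDs, ρ and the schedule are unknown.

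**What to change.** For each outcome, model the post-baseline score or scores on group and the participant's baseline score, adding time and group × time if there is more than one post-baseline visit. Report the adjusted yoga-minus-control difference at the final assessment, or at another visit named as primary, with a 95% CI from robust standard errors, small-sample corrected if N is small. State the number and timing of assessments and the working correlation.

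A GEE with a common baseline mean is an acceptable alternative only with a non-independence working correlation such as exchangeable. It can keep participants with missing scores, but GEE is not automatically valid when missingness depends on observed scores. In a deliberately adverse simulation (50 per arm, ρ = 0.5, true effect 0.50 SD, about 30% missing, dropout depending on baseline in opposite directions by arm), the completers' final-visit difference, which is what the independence version returns, averaged 0.76; the baseline-adjusted estimate averaged 0.50.

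Cost: no new data, plan wording, and one model per outcome in the software already chosen ("the researcher then used SPSS computer software version 20"). The statistical price is one estimated slope per outcome, 1/(N − 4) in variance: 1/36, about 3%, at N = 40. If the data have already been analysed, report this estimate labelled as specified afterwards.

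### Does the SAP's silence on the GEE contrast leave the yoga effect open to being halved?

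*Combined protocol and SAP*

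**What the plan says.** The Preface gives the research question as "The effect of a yoga intervention for reducing stress among people living with HIV during the covid-19 pandemic in Indonesia, a randomized controlled trial". Section 3 (Statistical analysis plan) contains all the analysis text:

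- **Model.** "This study took repeated assessments over time", and the study "used a Generalized Estimating Equation (GEE) approach to model each study outcome and to predict the relationship of the variables", allowing for correlation within a person.
- **Test level.** Alpha is 0.05, set "to determine the statistical significance of the variables".
- **Outcomes.** The data to be coded include "the perceived stress scale results brief health status survey, and coping self-efficacy".
- **Distribution.** Before modelling, the data for "independent and dependent variables was tested to determine its distribution and normality using plot histograms, logs and square roots, and checking residuals". Beyond this there is only a general remark: "GEE can handle correlated data with discrete, continuous, or binary outcomes".

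The section does not mention the yoga arm, the control arm or a contrast between them. It chooses no time point, analysis scale, distribution or link for any outcome. The only named assessments are in section 1 (Yoga protocol intervention), where an honorarium is paid "at the baseline and final assessments".

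**The concern.** Naming GEE does not by itself define a treatment effect. The wording fits a model with group and time terms as well as one with their interaction, and the coefficients mean different things. If baseline is an outcome row, the group coefficient without interaction averages the baseline difference, which randomisation makes zero in expectation, with the later differences. With the interaction and baseline as reference visit, the group coefficient estimates only the baseline difference. An analyst who read off the wrong coefficient would understate the yoga effect or miss it. An analyst who chose between coefficients after seeing the results would exceed the 5% level. The mention of logs and square roots raises a similar question about the scale on which the effect is estimated.

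**Working it through.** **Inputs from the documents.** Alpha 0.05 and a GEE for each outcome (section 3); randomised design (Preface); baseline and final assessments, named only for the honorarium (section 1). No sample size, SD, effect, power or correlation is given, so there is no planned figure to reproduce.

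**Assumed inputs.** n = 40 per arm, SD σ = 6 at each visit, final-visit effect δ = 3, two-sided test, within-person correlation ρ from 0 to 0.7.

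**1. What each coefficient estimates** (identity link, complete data, baseline and final as outcome rows).

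- Group term, no interaction: the mean of the two arm differences, (0 + δ)/2 = 1.5.
- Group-by-time term: δ − 0 = 3.
- Final score adjusted for baseline: δ = 3.

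Simulated GEEs with a true final effect of 1.0, 4,000 per arm and ρ = 0.5 gave 0.51 for the group term and 1.00 for the interaction. Baseline adjustment gave 0.99.

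**2. How far one half depends on the conditions.** With complete data, the group term is the average arm difference over all visits, baseline included.

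- Three visits: (0 + 1 + 1)/3 = 2/3 if the effect is full at both follow-ups; (0 + 1/2 + 1)/3 = 1/2 if it grows linearly; (0 + 0 + 1)/3 = 1/3 if it appears only at the last visit.
- Four visits: 3/4 if constant after baseline; 1/2 if linear.
- Two visits with 20% or 40% dropout at the final visit: single simulation runs gave 0.45 to 0.47 and 0.33 to 0.36.
- Baseline as a covariate: about 1, so no dilution.

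**3. Power under the assumed inputs.** Group-by-time: SE = σ√(2(1−ρ))·√(2/n). Group term: SE = σ√((1+ρ)/2)·√(2/n). Power ≈ Φ(estimate/SE − 1.96).

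| ρ | Group-by-time SE | Power | Group-term SE | Power |
|---|---|---|---|---|
| 0 | 1.897 | 35% | 0.949 | 35% |
| 0.3 | 1.587 | 47% | 1.082 | 28% |
| 0.5 | 1.342 | 61% | 1.162 | 25% |
| 0.7 | 1.039 | 82% | 1.237 | 23% |

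The loss is nil at ρ = 0 and large only at moderate to high correlation. For comparison, baseline adjustment at ρ = 0.5 has SE = 6·√(1 − 0.25)·√(2/40) = 1.162 and power Φ(3/1.162 − 1.96) = 73%.

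**4. False positives.** In simulation under no effect, each test alone rejected in 5–6% of trials. With equal variances, a person's mean and change are uncorrelated, so reporting whichever is significant gives about 1 − 0.95² = 9.75% in large samples. Simulation at 30–60 per arm gave 10–11%. This excess needs selection after the fact; no single reading of the plan produces it.

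**5. Scale.** For near-normal scores, letting a residual check choose raw, square-root or log scale changed 0–0.2% of verdicts. For an assumed skewed distribution (gamma, shape 1.6, scale 6: mean 9.6, SD 6√1.6 = 7.6), choosing the scale gained about 3 points of power for a proportional effect and 33–35 points for an additive effect floored at zero. The answer depends on a score distribution the documents do not describe, so no size can be attached.

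**The case for a change.** The strongest argument for a change is that the omission is real and cheap to repair. The analysis section of a two-arm trial never mentions the arms, and alpha attaches to variables rather than to a comparison. Baseline and final are the only assessments the documents name, and with those two as outcomes the dilution is exactly one half. At assumed correlations of 0.3 to 0.7 and 30 to 60 per arm, the group term and the interaction reach different verdicts in 45–67% of simulated trials. A sentence of wording would close the gap.

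The omission stands, and so does the algebra. The step to a defect in the plan does not. The text neither states a model without interaction nor calls the group main effect the yoga effect. The two visits come from a payment clause, and the handling of baseline and the link are unstated. Every power figure rests on assumed inputs. The specific choices a repair would make are also trade-offs: group-by-time has 61% power against 73% for baseline adjustment in the case above, and fixing the raw scale costs almost nothing or a good deal depending on skewness. Finally, section 3 is written mostly in the past tense. If outcomes had already been examined, new wording could not restore pre-specification.

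**Conclusion.** The concern identifies missing detail, and no change to the plan follows. The SAP names a suitable family of models for repeated scores and leaves the contrast to the analyst. In a randomised trial, the ordinary ways to fill that gap are group-by-time at the final assessment or a comparison adjusted for baseline. Both estimate the full effect, at 1.00 and 0.99 of the true value in simulation. Exact halving needs two assessments, baseline as an outcome row, an identity link, complete data and a model without interaction, and the documents establish none of these. Outside those conditions the fraction in the cases examined runs from about 1/3 to 3/4, and is about 1 with baseline as a covariate. The inflation to 10–11% needs selective reporting, which nothing in the documents suggests. A reader of the results should check which contrast and scale were reported; that is a matter of clear reporting.
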